1.3.2 Other Biodegradable Ocular Implants

A number of sustained-release drug delivery implants using the Allergan biodegradable polylactic acid (PLA) and/or polylactic-*co*-glycolic acid (PLGA) NOVADUR[®] drug delivery system preceded the development of the Bimatoprost SR implant. The extensive clinical experience with previous intraocular implants demonstrates the safety and tolerability of an intraocular biodegradable implant administered into the eye via an applicator system. For example, late phase clinical trials of sustained-release implants have been completed for the OZURDEX[®] dexamethasone intravitreal implant using the NOVADUR drug delivery system for intraocular injections. Because Bimatoprost SR is similar to OZURDEX in a number of aspects and uses the NOVADUR drug delivery system for intraocular injections, these data may be supportive of the safety and tolerability of Bimatoprost SR in humans.

1.3.3 Clinical Study with Bimatoprost SR

Study 192024-041D was a Phase 1/2, paired-eye comparison evaluating the safety and efficacy of 4 dose strengths of Bimatoprost SR (6 µg, 10 µg, 15 µg, or 20 µg [2 × 10 µg implants]), as single or repeat administration in one eye (study eye), versus the use of topical LUMIGAN[®] 0.03% in the fellow eye (nonstudy eye). The objective of this study was to evaluate the safety and IOP-lowering efficacy of Bimatoprost SR in patients with OAG.

A total of 109 patients received a single administration and 24 patients received a repeat administration of Bimatoprost SR. A trend in dose-response was observed across the 4 dose strengths that were tested. Data suggest that the implant may provide topical prostaglandin analog-like efficacy up to 3 to 4 months post-implantation in the majority of patients. Data following the second administration in the redosed patients showed similar IOP lowering to that observed following the first administration of Bimatoprost SR.

Bimatoprost SR showed an acceptable safety profile with single and repeat administrations in Study 192024-041D. Most adverse events were ocular, mild or moderate in severity, occurred within the first 2 days after Bimatoprost SR administration, and were considered related to the study drug administration procedure. There were no reports of serious study drug-related adverse events, and no new safety concerns were observed after the second treatment. Please refer to the Investigator's Brochure for details on reported safety findings.

1.4 Study Rationale

In the 192024-041D Phase 1/2 clinical study, results suggest that Bimatoprost SR provides IOP-lowering efficacy similar to topical prostaglandin analogs in the dose strengths proposed

for this Phase 3 investigation. Additionally, the safety profile of Bimatoprost SR at dose strengths of 20 µg (2 × 10 µg) or less in the Phase 1/2 study was acceptable, and supports additional clinical study in man. Study 192024-092 is a randomized, patient and efficacy evaluator-masked, parallel-group comparison to evaluate the safety and IOP-lowering effects of repeated administrations of 10 µg or 15 µg Bimatoprost SR in patients with OAG or OHT and open iridocorneal angles inferiorly in the study eye by clinical gonioscopy.

The 2 dose strengths of Bimatoprost SR will be compared versus a control group treated with the active comparator, topically applied timolol 0.5%. Timolol is a well-established treatment for IOP lowering in glaucoma and OHT, and has been used as a comparator in other IOP-lowering studies ([Weinreb and Kaufman, 2009](#)).

2. Study Objectives and Clinical Hypotheses

2.1 Study Objectives

- To evaluate the IOP-lowering efficacy and safety of 2 dose strengths of Bimatoprost SR in patients with OAG or OHT after initial and repeated administrations

2.2 Clinical Hypotheses

- At least 1 dose strength (10 µg or 15 µg) of Bimatoprost SR will have an IOP-lowering effect that is noninferior to that of topically administered timolol maleate 0.5% (hereafter referred to as timolol) eye drops in patients with OAG or OHT following single and repeat administrations.
- Bimatoprost SR administered intracamerally in dose strengths of 10 µg or 15 µg will have an acceptable safety profile in patients with OAG or OHT, following single and repeat administrations.

3. Study Design

This study is a multicenter, dose-ranging, randomized, parallel-group, patient and efficacy-evaluator masked 52-week evaluation (52-week treatment period with 8 months extended follow-up) of the safety and efficacy of Bimatoprost SR compared to timolol twice daily (BID) in patients with OAG or OHT. The patients and the evaluators of the primary endpoint (IOP) will be masked to the treatment received. The site coordinator and designated staff will not be masked to whether the patient received 1 of the two dose strengths of Bimatoprost SR or the Sham administration, but will be masked to the specific dose strength that the patient receives. Vehicle eye drops will be used BID to mask the treatment of

patients receiving Bimatoprost SR in the study eye. The fellow eye will receive a Sham administration plus topical timolol eye drops BID. Control group patients will receive a Sham administration plus timolol in both eyes (see Table 7). The study will be conducted at approximately 180 sites globally.

Two Bimatoprost SR dose strengths (10 µg or 15 µg) will be tested in this study. Patients will receive a scheduled second administration of Bimatoprost SR at 16 weeks following the first administration and a third scheduled administration at 16 weeks following the second administration (ie, 32 weeks after the initial administration). Control group patients will receive Sham administrations at all administration visits.

Table 7 Treatment Groups

| Treatment | Study Eye Treatment | Fellow Eye Treatment |
|----------------------|-------------------------------|-------------------------------|
| Bimatoprost SR 10 µg | Dose strength: 10 µg | Sham administration procedure |
| | Eye drops: Vehicle BID | Eye drops: Timolol BID |
| Bimatoprost SR 15 µg | Dose strength: 15 µg | Sham administration procedure |
| | Eye drops: Vehicle BID | Eye drops: Timolol BID |
| Control | Sham administration procedure | Sham administration procedure |
| | Eyedrops: Timolol BID | Eyedrops: Timolol BID |

BID = twice daily

Patients will begin self-administration of the study-provided eye drops in both eyes starting with the evening dose on the first administration (Day 1) visit (at which they will receive Bimatoprost SR administration or Sham administration). Patients will continue self-administration of study-provided eye drops in the morning (at 08:00 ± 1 hour) and in the evening (at 20:00 ± 1 hour), which is approximately 12 hours apart. Patients will be instructed not to administer their drops on the morning of a study visit. Drops will be administered immediately after the Hour 0 IOP measurement.

The duration of the study for each patient is approximately 22 months (screening duration of up to 28 days before washout, plus washout of up to 42 days before the first administration, plus the 52-week treatment period, plus 8 months extended follow-up). Patients will be followed for at least 12 months after their last Bimatoprost SR (or Sham) administration, and may exit early at or after the twelfth month following the last administration if there are no safety concerns in the opinion of the investigator.

4. Study Population and Entry Criteria

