| Table 3 | Administration Cycle 1 Schedule of Visits and Procedures: Treatment Period Day 2 through Week 12 | 17 |
| Table 4 | Administration Cycle 2 Schedule of Visits and Procedures: Treatment Period Week 15 Through Week 28..... | 18 |
| Table 5 | Administration Cycle 3 Schedule of Visits and Procedures: Treatment Period Week 31 Through Week 52..... | 20 |
| Table 6 | Schedule of Visits and Procedures: Extended Follow Up Months 14, 16, 18, and 20..... | 22 |

Table 7 Treatment Groups 30

Table 8 Minimum Washout Period by Ophthalmic Medication Class 63

List of Figures

Figure 1 Flowchart of Patient Participation 14

Approval Date: 05-Jun-2018

Protocol Summary

Study Compound: Bimatoprost sustained-release (SR) biodegradable implants containing preservative-free AGN-192024 (bimatoprost)

Phase: 3

Study Objectives:

To evaluate the intraocular pressure (IOP)-lowering efficacy and safety of 2 dose strengths of Bimatoprost SR in patients with open-angle glaucoma (OAG) or ocular hypertension (OHT) after initial and repeated administrations

Clinical Hypotheses:

At least 1 dose strength (10 µg or 15 µg) of Bimatoprost SR will have an IOP-lowering effect that is noninferior to that of topically administered timolol maleate 0.5% (hereafter referred to as timolol) eye drops in patients with OAG or OHT following single and repeat administration.

Bimatoprost SR administered intracamerally in dose strengths of 10 µg or 15 µg will have an acceptable safety profile in patients with OAG or OHT following single and repeat administration.

Study Design

Structure: Phase 3, multicenter, randomized, masked, parallel-group comparison (2 dose strengths of Bimatoprost SR versus active control), repeat administration

Duration: Approximately 22 months, consisting of screening of up to 28 days before washout, washout period of up to 42 days before initial administration of study medication, 52-week treatment period, plus 8 months extended follow-up

Study Treatment Groups: Bimatoprost SR dose groups: 10 µg and 15 µg

Control: Timolol eye drops plus Sham needleless procedure (that involves touching the eye at the area of insertion with a needleless applicator).

Dosage/Dose Regimen: Patients will receive 1 of 2 dose strengths of Bimatoprost SR or Control treatment in the study eye on Day 1 (with repeat administration of the same dose strength or Sham at Week 16 and Week 32).

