5.4 Treatment Allocation Ratio and Stratification

Randomization to treatment groups will use a 1:1:1 ratio. Patients will be randomized to receive Bimatoprost SR (either 10 µg or 15 µg) plus vehicle eye drops, or a Sham administration procedure plus timolol eye drops, in the study eye. Randomization will be stratified by Baseline study eye Hour 0 IOP (≤ 25 mm Hg or > 25 mm Hg).

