7.7 Sample Size Calculation

The sample size calculation is based on the primary efficacy analysis of the IOP for US FDA review since the sample size based on the primary efficacy analysis for other regions is expected to be smaller.

The initial sample size was estimated based on a 2-sided t-test with $\alpha = 0.05$ at each timepoint and the assumption that the mean IOP difference between Bimatoprost SR 10 μg and timolol is -0.25 mm Hg (ie, Bimatoprost SR 10 μg is 0.25 mm Hg better in IOP-lowering than timolol) at Weeks 2 and 6 and 0 mm Hg at Week 12, with a common standard deviation of 4.0 mm Hg and a common within-subject correlation of 0.6. It was also assumed that the efficacy (IOP-lowering effect) of Bimatoprost SR 15 μg is better than that of Bimatoprost SR 10 μg by 0.25 mm Hg at each timepoint (Hours 0 and 2). These assumptions were made at the study design phase based on the data obtained from the ongoing clinical study 192024-041D. Based on simulations, a sample size of 540 patients (180 per group) would provide approximately 95% and 81% power to show noninferiority (NI) of Bimatoprost SR 15 μg and Bimatoprost SR 10 μg , respectively, to timolol at all 6 scheduled timepoints based on an NI margin of 1.5 mm Hg and at 3 or more timepoints based on an NI margin of 1.0 mm Hg. Assuming a premature discontinuation rate of 10% within 12 weeks (before primary database lock), approximately 600 patients (200 per group) were to be enrolled into this study.

As part of ongoing centralized data monitoring of masked study data, some of the initial assumptions used for sample size calculation have been revisited. The rate of discontinued or rescued patients in the first 12 weeks is approximately 5%, which was less than the rate of 10% assumed at the study design phase. Furthermore, the masked common IOP variability (pooled standard deviation across treatments and timepoints) is approximately 3.8 mm Hg, which was also less than the assumed 4.0 mm Hg at the study design phase. With the updated

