10.4 ADDITIONAL EFFICACY PARAMETERS

11.0 SAFETY ANALYSES

The safety analysis will be performed using the safety population. The safety parameters will include the following nonocular safety parameters: nonocular AEs, clinical laboratory values, vital signs, and pregnancy; and ocular safety parameters: ocular AEs, implant/sham assessment, visual acuity, visual field examination, macroscopic iris color assessment, macroscopic conjunctival hyperemia assessment, Bimatoprost SR implant assessment, biomicroscopic examination, lens assessment, optic disc examination, dilated ophthalmoscopic examination, gonioscopy assessment, optical coherence tomography (OCT), specular microscopy, pachymetry, anterior segment optical coherence tomography (AS-OCT). Unless otherwise stated, the last nonmissing safety assessment before the first dose of study treatment will be used as the baseline for all analyses of that safety parameter. Continuous variables will be summarized by number of patients and mean, SD, median, the 1st quartile and the 3rd quartile, minimum, and maximum values. Categorical variables will be summarized by number and percentage of patients.

For ocular safety assessments, analyses will be performed by treatment group for study eye and pooled for fellow eye based on the first actual treatment received in each eye. For nonocular safety measures, analyses will be performed on a patient basis for the treatment actually received.

For all safety by-cycle summary analyses, in order to compare cycles of similar duration, the data included in each cycle will be,

- Cycle 1 (16 weeks): data from the 1st injection to the 2nd injection date -1 or upper bound of week 15 visit window (section 16.1) if a patient didn't receive the 2nd injection;
- Cycle 2 (16 weeks): data from the 2nd injection to the 3rd injection date -1 or upper bound of week 31 visit window (section 16.1) if a patient didn't receive the 3rd injection;
- Cycle 3 (20 weeks): data from the 3rd injection to upper bound of week 52 visit window (section 16.1);
- Extended safety follow up: data after week 52 for patients with 3 injections and extended follow up.

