11.3.12 Specular Microscopy

Endothelial cell density will be assessed using specular microscopy performed on the central cornea for each eye at Screening, Week 12, Week 28, Week 44, Week 52, and Month 20/Exit. At each examination, average endothelial cell density for each eye will be reported by reading center and used for analysis.

Endothelial cell density baseline and changes from baseline, and raw values will be summarized descriptively by visit for each treatment group in study eyes and pooled for the fellow eyes.

In addition, the number and percentage of patient eyes who reported 1) within ± 200 cells/ mm^2 change; 2) $\geq 10\%$ loss; 3) $\geq 20\%$ loss; 4) $\geq 30\%$ loss; 5) $\geq 40\%$ loss; and 6) $\geq 50\%$ loss in endothelial cell density will be summarized by visit for each treatment group in study eyes and pooled for fellow eyes respectively for each category.

Fellow eye-adjusted endothelial cell density changes from baseline and percent loss from baseline values in the study eye are defined below.

- Fellow eye-adjusted endothelial cell density change from baseline (CFB_ADJ) is defined as the difference in endothelial cell density change from baseline between the study eye and the fellow eye, and calculated as $CFB_ADJ = CFB_SE - CFB_FE$, where CFB_SE is endothelial cell density change from baseline in the study eye and CFB_FE is endothelial cell density changes from baseline in the fellow eye.
- Fellow eye-adjusted endothelial cell density percent loss from baseline (PLoss_ADJ) is defined as the difference in endothelial cell density percent loss from baseline between the study eye and the fellow eye, and calculated as $PLoss_ADJ = PLoss_SE - PLoss_FE$, where PLoss_SE is endothelial cell density percent loss from baseline in the study eye and PLoss_FE is endothelial cell density percent loss from baseline in the fellow eye.

Fellow eye-adjusted endothelial cell density will be summarized descriptively by visit for each treatment group, and the number of patients who reported changes within ± 200 cells/mm² will also be summarized.

Additionally, the number and percentage of patients who reported 1) $\geq 10\%$ loss; 2) $\geq 20\%$ loss; 3) $\geq 30\%$ loss; 4) $\geq 40\%$ loss; and 5) $\geq 50\%$ loss in fellow eye-adjusted endothelial cell density percent loss will be summarized by visit for each treatment group for each category, respectively.

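### Corneal harm is planned only as per-arm descriptive summaries, with no between-arm estimate and no confidence interval, although the trial states a safety hypothesis for both doses

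*Protocol*

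**What the plan says.** Protocol 3 opens with "This study is a multicenter, dose-ranging, randomized, parallel-group, patient and efficacy-evaluator masked 52-week evaluation" and names safety as well as efficacy in the comparison with timolol. The Protocol Summary gives the structure as a "parallel-group comparison (2 dose strengths of Bimatoprost SR versus active control), repeat administration". Protocol 2.2 states that each strength "will have an acceptable safety profile in patients with OAG or OHT, following single and repeat administrations", without a threshold. Allocation is equal across the three arms (Protocol 5.4).

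The safety method is set in SAP 11.0. Continuous variables get n, mean, SD, median, quartiles and range. For the rest, "Categorical variables will be summarized by number and percentage of patients". The corneal parts follow this pattern:

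- SAP 11.3.12 summarises endothelial cell density (raw value and change from baseline) by visit and arm. It adds the share of eyes within ±200 cells/mm² and the shares at five loss thresholds from 10% to 50%: loss in "endothelial cell density will be summarized by visit for each treatment group in study eyes and pooled for fellow eyes". Fellow eye-adjusted change and percent loss, the coefficient of variation and pleomorphism are also summarised per arm.
- SAP 11.3.11 summarises corneal thickness and its change per arm.
- SAP 11.1 tabulates corneal events of special interest by preferred term and arm, and by cycle.

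None of these sections specifies a difference between arms or an interval.

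**The concern.** The plan treats the cornea as a main safety question. Protocol 1.3.1 reports that monkeys did not tolerate the strengths tested because the implant stayed in contact with the corneal endothelium. Endothelial cell density is an entry criterion, corneal events are of special interest, and SAP 11.3.7 counts patients with implant-endothelium contact.

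Efficacy gets model-based differences, 95% CIs, margins and a testing order. Corneal harm gets one column per arm, and the reader must judge the gaps by eye. Two misreadings become easy: a chance gap between 15 µg and 10 µg taken as dose-related, and an arm with no events taken as free of risk. An interval guards against both. Specifying it before the results are seen also fixes the visits, thresholds and baseline adjustment.

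**Working it through.** **The plan's own figure.** The stated power is 95.1% (15 µg) and 83.5% (10 µg) with 162 per group and SD 3.8 mm Hg (Protocol 7.7). A simulation of 20,000 trials used six equally correlated timepoints (correlation 0.6), the planned mean differences and pooled two-sided 95% t-intervals. Success meant all six upper limits ≤ 1.5 and at least three ≤ 1.0 mm Hg. It gave 95.2% and 83.6%. The efficacy sizing is not in dispute. It concerns IOP only and says nothing about precision for corneal harm.

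**Where intervals are planned.** SAP 10.0 sets two-sided 95% intervals in the efficacy section, and SAP 10.1.1 and 10.3 apply them to IOP against timolol. SAP 11.0, 11.1, 11.3.11 and 11.3.12 ask for none.

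**What an interval would add.** Assumptions, because the documents give neither corneal event rates nor evaluable eyes at Week 52 or Month 20: 162 eyes per arm (the IOP completer number, borrowed as a round figure) and invented counts.

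The Newcombe interval for d = p1 − p2 uses each arm's Wilson limits (l, u):

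- Wilson: [p + z²/2n ± z√(p(1−p)/n + z²/4n²)] / (1 + z²/n), with z = 1.96
- lower = d − √((p1−l1)² + (u2−p2)²)
- upper = d + √((u1−p1)² + (p2−l2)²)

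For 16 versus 8 eyes:

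- p1 = 16/162 = 0.0988, Wilson 0.0617 to 0.1544
- p2 = 8/162 = 0.0494, Wilson 0.0252 to 0.0944
- d = 8/162 = 0.04938
- lower = 0.04938 − √(0.0371² + 0.0450²) = 0.04938 − 0.05831 = −0.0089
- upper = 0.04938 + √(0.0556² + 0.0242²) = 0.04938 + 0.06066 = 0.1100

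The planned table would show 9.9% and 4.9%. The interval adds that the 4.9-point gap is compatible with anything from −0.9 to 11.0 points. The same method over a range of counts gives:

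| Eyes (of 162 each) | Difference, points | 95% CI |
|---|---|---|
| 8 vs 2 | 3.7 | −0.3 to 8.3 |
| 16 vs 8 | 4.9 | −0.9 to 11.0 |
| 16 vs 2 | 8.6 | 3.8 to 14.3 |
| 24 vs 8 | 9.9 | 3.4 to 16.6 |
| 32 vs 16 | 9.9 | 2.1 to 17.6 |

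**Zero events.** The exact two-sided 95% upper limit is 1 − 0.025^(1/n). For n = 162 it is 0.0225, or 2.3%. For the planned enrolment of 170 it is 2.1%.

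**Not a test.** For assumed true rates of 10% and 5%, power at 162 per arm is about 40%, and 80% power would need 435 per arm. The intervals serve to show imprecision, not to decide a hypothesis.

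**The case against.** The strongest case against is that descriptive safety reporting is common, the trial is not sized for safety, and nothing in the documents requires inference on harm. Table specifications sit in a separate document (SAP 4.0), so intervals could appear there. Readers can also compute crude intervals from the printed n, means, SDs and counts. All of this stands, and it keeps the point minor. It does not remove it: a baseline-adjusted difference cannot be rebuilt from summary tables, and the SAP text does not call for one.

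A reader might infer four stronger things that the documents do not support:

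- *That safety rests on bare percentages.* It does not. Means, SDs, quartiles, changes from baseline and fellow eye-adjusted loss are planned. The fellow-eye adjustment is a contrast within patients, summarised per arm. What is absent is a comparison between arms.
- *That a dose will be chosen from these summaries.* No section says that this trial selects a dose, and no selection rule is given. The efficacy hypothesis needs at least one strength to be noninferior to timolol. The design label in Protocol 3 does not promise a dose-to-dose contrast.
- *That the contrasts would be unbiased because the arms are randomised.* SAP 11.0 analyses ocular safety by the first treatment actually received. Under Protocol 5.6.1, a Bimatoprost SR study eye given nonstudy IOP-lowering medication gets Sham at later administrations, and patients medicated in both eyes get none. Under Protocol 8.8, such patients, and those who miss an administration, may leave 12 months after the last one and then complete the Month 20/Exit procedures. Exposure and timing therefore differ, most of all at Month 20. Investigators also view the implant on gonioscopy (Protocol 6.2), so masking does not fully protect event reporting against Control.
- *That no dose-to-dose IOP comparison is planned.* SAP 10.4 and Protocol 7.3.3 show headings without readable text, so this cannot be said. The corneal sections are readable.

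**Conclusion.** The point holds as a low-cost improvement. For corneal harm, the readable SAP plans per-arm description only, with no between-arm estimate and no interval, in a trial that compares safety with timolol and states a safety hypothesis for both doses. No efficacy conclusion is affected and no stated number is wrong.

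The size is illustrative. At about 162 eyes per arm, a doubling from 4.9% to 9.9% would not exclude zero, 4.9% against 14.8% (8 versus 24 eyes) would, and a zero count leaves up to 2.3% open. These figures rest on invented counts and on a denominator derived from 12-week IOP completion. The numbers evaluable at Week 52 and Month 20 are not given; if they are smaller, the intervals at the same proportions will be wider.

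**What to change.** In SAP 11.3.12, for study eyes at Week 52 and Month 20, add each dose minus Control and 15 µg minus 10 µg, with 95% CIs, for:

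- mean percent change in endothelial cell density, adjusted for baseline density;
- the proportions with 20% or more and with 30% or more loss (Newcombe), with an exact CI for each arm's proportion.

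In SAP 11.1, add the same proportion differences for corneal events of special interest.

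Show the number of eyes analysed per arm and visit. Report the contrasts by randomised arm as well as by treatment received. State that Sham substitution and early exit limit interpretation, most of all at Month 20. Label the intervals descriptive, without multiplicity adjustment.

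The cost is SAP wording and extra columns; no patients, visits or alpha are needed. The downside is several unadjusted intervals. The density items alone give 3 contrasts × 3 measures × 2 visits = 18, of which about 18 × 0.05 = 0.9 would exclude zero by chance if the arms did not differ. The descriptive label must therefore stand beside the tables.
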